8.1 Statistical Hypotheses

Statistical hypothesis (non-inferiority test):

Null hypothesis: The point prevalence of low disease activity (ASDAS<2.1) in both “Remote monitoring” and “Patient-initiated care” is more than 15 percentage points lower than in “Usual care” arm at any follow-up time point.

Alternative hypothesis: The point prevalence of low disease activity (ASDAS<2.1) in “Remote monitoring” / “Patient-initiated care” is at most 15 percentage points lower than in “Usual care” arm at any follow-up time point.

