8.2 Sample Size Determination

Randomly assigning 80 participants to each of the three study arms will give approximately 80% power to conclude that at least one of the alternative follow-up strategies is non-inferior to conventional follow-up, using a 15% non-inferiority margin. This controls for multiple testing at the 5% level and assumes an analysis based on a logistic mixed model. We will additionally test the non-inferiority of “Patient-initiated care” to “Remote monitoring” using the same 15% margin. This test will be done only if “Patient-initiated care” is shown to be non-inferior to conventional care (a hierarchical test), and thus will not inflate the 5% false positive rate.

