8.4.1 General Considerations

- Efficacy (both primary and secondary endpoints) and safety analyses will include data from all randomised patients who started the allocated intervention by attending at least one completed questionnaire and blood test result after randomisation (FAS), and robustness analyses will be performed in the PPS.
- Demographics, baseline characteristics, efficacy and safety variables will be summarised using descriptive statistics.
- All efficacy analyses will be presented with the results from the hypothesis testing (by p-value) in addition to estimates and 95% confidence limits of the treatment effect. For the primary variables specifically, this will be the estimated mean probability with corresponding 95% confidence limits.

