8.4.2 Primary Endpoint

The primary endpoint is defined as the point prevalence of with low disease activity (defined as ASDAS <2.1) at the 6-, 12- and 18-months follow-ups.

The probability of being in low disease activity for repeated measures per individual will be used to estimate a risk difference across the three study arms. The primary variables will be analyzed using logistic regression mixed models with allocated study arm as primary explanatory variable. Other pre-specified covariates included in sensitivity analyses include age, gender, disease features. The SAP will detail these procedures, as well as alternative and further supportive evaluations, such as analyses including unbalanced baseline predictors or modifications of the regression model in case validity assumptions are not met. The primary analysis will be performed in the FAS. The primary endpoint will be evaluated by the p-value and confidence interval of the hypothesis test from the regression analysis.

In case the null hypothesis is not rejected, the new, follow-up strategies will be considered worse or inferior to usual care with hospital follow-up visits.

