8.4.3 Secondary Endpoint

Between-group comparisons will be performed for secondary efficacy endpoints.

The between-group comparisons for secondary endpoints will be tested as for the primary endpoint where applicable and additional analyses will be performed based on the following methods (but not limited to):

- Continuous secondary variables will be subject to repeated measures mixed models or appropriate non-parametric alternatives
- Binary response variables will be analyzed using logistic regression (possibly adjusting for within-subject dependencies by mixed model approaches) or other appropriate tests, e.g., chi-square/Mantel-Haenszel test

Unless otherwise specified, all statistical hypotheses will be tested as the primary endpoint, i.e., with an assessment of non-inferiority based on the p-value of the group differences.

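### Sections 8.4.1 and 8.4.3 describe the primary interval and the primary test in terms that cannot be set against the 15-point margin of 8.1, and leave secondary non-inferiority tests with no margin

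*Protocol*

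**What the plan says.** Section 8.1 labels the hypothesis as one for a non-inferiority test. The null is that low disease activity under the new strategies "is more than 15 percentage points lower than in “Usual care” arm at any follow-up time point"; the alternative is that it "is at most 15 percentage points lower than in “Usual care” arm at any follow-up time point". Section 8.2 sizes the trial to conclude that at least one new strategy "is non-inferior to conventional follow-up, using a 15% non-inferiority margin".

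Section 8.4.2 says that a risk difference between the arms will be estimated and that the model is a logistic mixed model with study arm as the main explanatory variable. It then says: "The primary endpoint will be evaluated by the p-value and confidence interval of the hypothesis test from the regression analysis". If the null is not rejected, the new strategies are to be regarded as worse or inferior.

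Section 8.4.1 first asks for p-values, estimates and 95% limits of the treatment effect in all efficacy analyses. It then makes a specific provision for the primary endpoint: "For the primary variables specifically, this will be the estimated mean probability with corresponding 95% confidence limits".

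Section 8.4.3 says that, unless specified otherwise, all hypotheses are to be "tested as the primary endpoint, i.e., with an assessment of non-inferiority based on the p-value of the group differences".

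The 15-point margin is not named anywhere in 8.4.

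**The concern.** The margin is a difference between two arms on the probability scale. To use it, the plan needs an interval for that difference, or a p-value computed at -15 points. Section 8.4.2 is compatible with this, but the sentences on either side of it are not.

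The sentence in 8.4.1 replaces the treatment effect, for the primary endpoint, with a quantity that belongs to one arm. That contradicts the risk difference in 8.4.2. Two separate arm intervals also do not give the limit that has to be compared with -15 points.

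The sentence in 8.4.3 reports how the primary endpoint is tested, and the ordinary meaning of its words is a p-value for a difference of zero. The arm coefficient of a logistic mixed model has exactly such a p-value by default, on the log-odds scale. For the primary endpoint a reader can repair the wording by going back to 8.1. For secondary endpoints no repair is possible, because the protocol gives no margin for any of them. A non-significant difference could then be reported as non-inferiority.

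At stake is whether two analysts who follow the same protocol reach the same conclusion from the same data.

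**Working it through.** 1. **The passages side by side.** Quantity with a margin: the risk difference (8.1, 8.2). Quantity to be estimated: the risk difference (8.4.2). Quantity given 95% limits as the primary result: the mean probability (8.4.1). Basis of the non-inferiority assessment: the p-value and interval of the hypothesis test (8.4.2), or the p-value for group differences (8.4.3). Only the first two and the 8.4.2 rule, read with 8.1, fit together.

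2. **The plan's own figure.** Section 8.2 states about 80% power with 80 per arm. It gives no event rate, sidedness, within-patient correlation or drop-out, so the figure can only be bracketed. For one comparison at one visit with a true difference of 0, power = Φ(0.15/√(2p(1-p)/80) - z). At p = 0.88 and one-sided 0.025 this is Φ(0.15/0.0514 - 1.96) = 83.1%. For at least one of two comparisons (correlation 0.5 from the shared control arm), power at 88% is 96.7%, 93.2% and 88.0% at one-sided 0.05, 0.025 and 0.0125. Values near 80% need other inputs, for example a rate of 80% at 0.025 (81.2%) or 85% at 0.0125 (81.3%). The stated power is neither confirmed nor refuted, and it does not decide this point.

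3. **Can the two readings give different verdicts?** Inputs: 80 per arm (8.2), margin 15 points (8.1), and usual care 88%. The 88% is the database figure in 3.2 and is used here as an assumption. One visit, unpooled normal approximation, SE = √(p₁(1-p₁)/80 + p₂(1-p₂)/80).

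   - Observed 88% v 88%: SE = √(2 × 0.88 × 0.12/80) = 0.0514. Zero-difference p = 1.00. Non-inferiority z = 0.15/0.0514 = 2.92, one-sided p = 0.0018. The 95% interval is -10.1 to +10.1 points, so non-inferiority is shown.
   - Observed 88% v 80%: SE = √(0.88 × 0.12/80 + 0.80 × 0.20/80) = 0.0576. Zero-difference z = 0.08/0.0576 = 1.39, two-sided p = 0.165. Non-inferiority z = (-0.08 + 0.15)/0.0576 = 1.21, one-sided p = 0.112. The 95% interval is -8 ± 11.3, that is -19.3 to +3.3 points, so non-inferiority is not shown.

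   The second case splits: there is no significant difference, and non-inferiority is not shown. Its p-value of 0.112 exceeds 0.05, 0.025 and 0.0125, so the unstated sidedness and multiplicity adjustment do not change the result.

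4. **What arm-level limits show in the same case.** Usual care: 88 ± 1.96 × √(0.88 × 0.12/80) = 88 ± 7.1, that is 80.9% to 95.1%. New strategy: 80 ± 1.96 × √(0.80 × 0.20/80) = 80 ± 8.8, that is 71.2% to 88.8%. The intervals overlap, and neither contains a number that can be compared with -15 points.

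5. **Size of the misreading, if p > 0.05 were taken as non-inferior.** True rates 88% v 73%, one visit, Wald test of the log odds ratio. Log odds ratio = ln(0.88/0.12) - ln(0.73/0.27) = 0.998. SE = √(1/(80 × 0.88 × 0.12) + 1/(80 × 0.73 × 0.27)) = 0.426. z = 2.34, so p < 0.05 in Φ(2.34 - 1.96), about 65% of trials, and p > 0.05 in about 35%. This is the cost of misreading the text. It is not an error rate of the rule in 8.4.2.

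**The case against.** A reader might infer that the primary test as planned asks only whether there is any difference, so that the trial's main conclusion rests on the wrong null. The protocol does not support that. The only null it states is the 15-point null in 8.1, and 8.2 repeats the margin and ties it to the logistic mixed model. The hypothesis test named in 8.4.2 most naturally means that one. The consequence attached to it, that failing to reject means inferior, makes sense only for a margin null: under a zero-difference null, two equal arms would be called inferior about 95% of the time. It also rules out treating p > 0.05 as success on the primary endpoint.

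Three further points on the other side have weight. The sentence in 8.4.1 just before the mean-probability one does ask for 95% limits of the treatment effect, and the passage concerns presentation. A p-value for a group difference could be one computed against a margin. And 8.4 calls itself a summary, with technical detail left to the SAP.

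These arguments dispose of the stronger reading. They do not remove what is written. The sentence in 8.4.1 singles out the primary endpoint and gives it a different quantity from 8.4.2. The sentence in 8.4.3 extends the primary test to hypotheses for which no margin exists, so there the only reference value in the text is zero. Both are statements in the protocol that an SAP author would have to contradict, not details left open.

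**Conclusion.** The point holds as an inconsistency of wording between 8.1, 8.2 and 8.4.2 on one side and 8.4.1 and 8.4.3 on the other. It does not show that the primary test is the wrong one. Section 8.4.1 attaches the primary 95% limits to a quantity that cannot be compared with the margin. Section 8.4.3 describes the test in words that literally mean a zero-difference test, and it leaves secondary non-inferiority assessments with no margin at all.

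The size is best shown by the split case: at 88% v 80% with 80 per arm, p = 0.165 for no difference, but an interval of -19.3 to +3.3 points. If the text were misread so that p > 0.05 meant non-inferior, about 35% of trials with a true 15-point deficit would pass at a single visit. Both figures assume 88% for usual care, one visit, no drop-out and a normal approximation. The three-visit mixed model would give different numbers. The inconsistency itself depends on none of these assumptions. It should be corrected because these sentences govern how the main conclusion is reached and reported.

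**What to change.** - **8.4.2:** replace the evaluation sentence with an explicit rule. Non-inferiority is concluded if the lower confidence limit, at the multiplicity-adjusted level of 8.2, of the model-based risk difference (new strategy minus usual care) lies above -15 percentage points. Any p-value is computed against the -15-point null, not against an odds ratio of 1. The same form serves the hierarchical comparison in 8.2, as patient-initiated care minus remote monitoring.
- **8.4.1:** make the primary estimate the risk difference with its confidence interval, and keep the arm-level mean probabilities as description.
- **8.4.3:** remove the clause that bases non-inferiority on the p-value for group differences. Report secondary endpoints that have no margin as estimates with confidence intervals, without a non-inferiority claim.

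The method of standardisation and of the interval can stay in the SAP. The cost is a wording amendment to three paragraphs and matching SAP text. The risk difference is already planned from the same model, so its interval is minor extra programming. No new data or patients are needed.

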3.2 Scientific Rationale for Study Design

The study is designed to investigate if two, new follow-up strategies for patients with axSpA are non-inferior to the conventional follow-up strategy with hospital visits for maintaining a stable, low disease activity. Hence, a randomized, controlled design is required to provide a valid comparison. A non-inferiority design is chosen as the two, new follow-up strategies are likely to be less resource-intensive, but they may still not be inferior compared to conventional follow-up for maintaining a stable, low disease activity. Based on data from the NOR-DMARD database (ClinicalTrials.gov NCT01581294), 88% of the patients remained at a stable, low disease activity level (ASDAS >2.1) after two-year follow-up, hence, superiority may be difficult to achieve.

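### Section 8.4.2 reads a failed non-inferiority test as proof of inferiority, when it shows only that non-inferiority was not demonstrated

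*Protocol*

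**What the plan says.** Protocol section 8.1 sets up a non-inferiority test on the prevalence of low disease activity (ASDAS below 2.1). Under the null, the prevalence with the new strategies "is more than 15 percentage points lower than in" usual care; under the alternative, it "is at most 15 percentage points lower than in" usual care. Section 8.2 plans 80 patients per arm, "using a 15% non-inferiority margin", for "approximately 80% power to conclude that at least one of the alternative follow-up strategies is non-inferior" to conventional follow-up.

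Section 8.4.1 asks for p-values "in addition to estimates and 95% confidence limits of the treatment effect". Section 8.4.2 says the primary endpoint is judged on the p-value and confidence interval from the regression, and then fixes what a failed test means: "In case the null hypothesis is not rejected, the new, follow-up strategies will be considered worse or inferior to usual care" with hospital visits. The protocol contains no separate test of inferiority and no provision for an inconclusive result.

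**The concern.** A non-inferiority test has one positive conclusion: the deficit is smaller than the margin. When the null stands, a deficit above 15 points has not been excluded, but neither has a smaller deficit, equality, or an advantage for the new strategy. Section 8.4.2 treats this lack of proof as proof of the opposite.

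It is the protocol's only rule for the primary conclusion when the test fails. Following it would report a harm that the data do not show, in a trial meant to inform how follow-up is organised. Two features widen the problem. The sentence speaks of the new strategies together, although section 8.2 foresees that only one may succeed. And section 8.4.3 tests other hypotheses in the same way as the primary endpoint unless otherwise specified, so the same reading could carry over to secondary endpoints.

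**Working it through.** **Inputs.** Margin 15 percentage points (sections 8.1 and 8.2); 80 per arm (section 8.2). The only rate given is in section 3.2: "88% of the patients remained at a stable, low disease activity level" after two years. It comes from a registry and is not stated to be the planning rate. The protocol does not give the sidedness of alpha, its split between the two comparisons or the within-patient correlation, so results are shown at one-sided 5%, 2.5% and 1.25%.

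**The plan's own figure.** The stated power of about 80% for at least one strategy cannot be reproduced without those inputs. At 88% in all arms and a single visit, simulation gives about 95% (one-sided 2.5%) or 91% (1.25%). A power of 80% would correspond to a rate of roughly 77% or 83% respectively. The point here does not depend on that figure.

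**Step 1: one result.** Unpooled Wald interval: d = p_new − p_usual, SE = √[p_new(1−p_new)/80 + p_usual(1−p_usual)/80].

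Take 64/80 = 0.800 against 70/80 = 0.875. Then d = −0.075 and SE = √(0.8×0.2/80 + 0.875×0.125/80) = 0.0580.

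| One-sided level | Interval | Limits (points) |
|---|---|---|
| 5% | 90% | −17.0 to +2.0 |
| 2.5% | 95% | −18.9 to +3.9 |
| 1.25% | 97.5% | −20.5 to +5.5 |

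Every lower limit is below −15, so non-inferiority fails at each level (one-sided p against −15 points = 0.098). Every interval contains zero (two-sided p against zero = 0.20).

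**Step 2: the range of results affected.** Usual care fixed at 70/80, one-sided 2.5%:

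| New strategy | Difference (points) | 95% CI (points) | Reading |
|---|---|---|---|
| 67/80 | −3.75 | −14.6 to +7.1 | non-inferior |
| 66/80 | −5.0 | −16.0 to +6.0 | not shown; zero inside |
| 61/80 | −11.25 | −23.1 to +0.6 | not shown; zero inside |
| 60/80 | −12.5 | −24.4 to −0.6 | not shown; below zero, not beyond the margin |
| 47/80 | −28.75 | −41.8 to −15.8 | wholly beyond the margin |

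Section 8.4.2 gives one label to everything from 66/80 down. From 61 to 66 the interval includes zero. Only at 47/80 or fewer does it lie wholly below −15.

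**Step 3: how often a truly equal strategy fails (88% in both arms, one visit).** SE = √(2×0.88×0.12/80) = 0.0514, and P(fail) = Φ(z − 0.15/0.0514).

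| One-sided level | One comparison fails: formula | One comparison fails: simulated | Both fail: simulated |
|---|---|---|---|
| 5% | 10.1% | 9.8% | 2.1% |
| 2.5% | 16.9% | 16.6% | 4.8% |
| 1.25% | 24.9% | 24.5% | 8.7% |

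The normal approximation for both failing, with correlation 0.5 from the shared control arm, is higher: 3.3%, 6.8% and 12.0%. Among single failures at one-sided 2.5%, about 85% have an upper limit at or above zero and essentially none lie wholly below −15.

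**Step 4: three visits.** Averaging three visits multiplies the variance by (1+2ρ)/3. At one-sided 2.5% to 1.25%, one comparison fails in 2.1% to 4.0% (ρ = 0.3), 5.3% to 9.1% (ρ = 0.5) or 9.6% to 15.3% (ρ = 0.7). Both fail in about 0.4% to 6% over the same range of ρ and alpha.

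**Step 5: a small true deficit.** Assume 83% against 88%, a 5-point deficit that section 8.1 accepts. A single-visit comparison fails in 42.3%, 54.7% and 65.8% at one-sided 5%, 2.5% and 1.25%.

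**The case against.** The strongest reply concerns size. The null in section 8.1 is worded on both new arms, the power statement refers to at least one, and the challenged sentence is plural. Read literally, the label then applies only when neither strategy passes, so at equality the relevant single-visit figures are about 2% to 9%, or about 0.4% to 6% with three visits at one-sided 2.5% to 1.25%. This reading is possible but not settled, because the alternative in section 8.1 is written for each strategy. The single visit is also not the planned analysis, which is a mixed model over three visits, and the 83% rate in step 5 is an assumption. These points limit how often the error would occur. They do not make the sentence correct when it does.

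Second, the interval is part of the primary evaluation under section 8.4.2, so a reader would see the uncertainty. That is true, but the interval does not alter the verdict the protocol prescribes.

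Third, the rule errs on the side of caution towards reduced follow-up, and replacing one phrase would cure it. Caution is served equally well by saying that non-inferiority was not demonstrated, which withholds endorsement without asserting harm. That phrase is the core of the fix; the further criterion only says when inferiority may be claimed.

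**Conclusion.** The concern holds: the sentence in section 8.4.2 is wrong as written. Non-rejection of a null of more than 15 points' deficit supports only the statement that non-inferiority was not demonstrated. This follows from section 8.1 alone and needs no assumed rate, alpha or correlation; the 64/80 against 70/80 example fails at all three alpha levels with zero inside each interval.

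How often a truly equal strategy would be mislabelled does rest on assumptions: 88% in both arms, 80 analysed per arm and Wald intervals. Per comparison it is about 10% to 25% for one visit (one-sided 5% to 1.25%) and about 2% to 15% for a three-visit average (2.5% to 1.25%). It is lower if the label is taken to apply only when both strategies fail. If the planned power of about 80% was calculated at equality, which section 8.2 does not say, both would be so labelled in about 20% of trials (100% − 80%).

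The error runs only against the new strategies. It does not raise the rate of false non-inferiority claims or touch the test, margin, sample size or conduct. It should be fixed, but it does not threaten the design.

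**What to change.** Replace the sentence in section 8.4.2 with a rule for each strategy separately, at the confidence level that matches the multiplicity-controlled alpha:

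> If the null hypothesis is not rejected for a strategy, non-inferiority of that strategy has not been demonstrated. Inferiority beyond the margin is concluded only if the whole confidence interval for the risk difference (new strategy minus usual care) lies below −15 percentage points. Otherwise the result is inconclusive.

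An interval wholly below zero but not wholly below −15 points should be described as lower than usual care, beside the non-inferiority verdict and not as a further confirmatory claim.

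The cost is one sentence in the protocol, carried into the SAP, with no effect on conduct, sample size, alpha or data collection. Section 8.4 says the SAP will be final before un-blinding. The correction should be in place by then, because a later change could look driven by the results.

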8.4.3 Secondary Endpoint

Between-group comparisons will be performed for secondary efficacy endpoints.

The between-group comparisons for secondary endpoints will be tested as for the primary endpoint where applicable and additional analyses will be performed based on the following methods (but not limited to):

- Continuous secondary variables will be subject to repeated measures mixed models or appropriate non-parametric alternatives
- Binary response variables will be analyzed using logistic regression (possibly adjusting for within-subject dependencies by mixed model approaches) or other appropriate tests, e.g., chi-square/Mantel-Haenszel test

Unless otherwise specified, all statistical hypotheses will be tested as the primary endpoint, i.e., with an assessment of non-inferiority based on the p-value of the group differences.

8.4.4 Safety Analysis

Rates and type of adverse events and serious adverse events in all three study arms will be reported.

9 Supporting Documentation and Operational Considerations

